Subjects with at Least One Anaphylactic Reaction, Hypersensitivity or Infusion-Related Reactions Not Leading to Discontinuation of IP [1]	xx (xx.x%) xx					
System Organ Class 1 Preferred Term 1 Preferred Term 2 Preferred Term 3	xx (xx.x%) xx xx (xx.x%) xx xx (xx.x%) xx xx (xx.x%) xx	xx (xx.x%) xx xx (xx.x%) xx xx (xx.x%) xx xx (xx.x%) xx	xx (xx.x%) xx xx (xx.x%) xx xx (xx.x%) xx xx (xx.x%) xx	xx (xx.x%) xx xx (xx.x%) xx xx (xx.x%) xx xx (xx.x%) xx	xx (xx.x%) xx xx (xx.x%) xx xx (xx.x%) xx xx (xx.x%) xx	xx (xx.x%) xx xx (xx.x%) xx xx (xx.x%) xx xx (xx.x%) xx

AE = adverse event; IP = investigational product; MedDRA = Medical Dictionary for Regulatory Activities; n = number of subjects within each SOC/PT category; N = number of subjects per treatment group; IP = investigational product; PT = Preferred Term; SOC = System Organ Class; TEAE = treatment-emergent adverse event.

Final 1 2 | 04-Oct-2023 | Page 81 of 218

[1] Anaphylactic reactions, hypersensitivity or infusion-related reactions not leading to discontinuation of IP were included in table as they were categorized as AE of special interest under Protocol Amendment 4 (V5.0). Definition for AE of special interest changed from Amendment 6 (V6.0) onwards, including anaphylactic reactions, hypersensitivity or infusion-related reactions leading to permanent discontinuation of IP..

Note: Results are n (n/N * 100) m is number of events.

A TEAE is defined as AE with an onset at the time of or following the start of treatment with IP.

AEs were coded using MedDRA version 26.0. Subjects are counted once for each SOC and once for each PT.

[figure not shown]
AEs are displayed by descending frequency of SOC, then descending frequency of PT within SOC, based on 'All MEDI7352' column. Table is sorted by international order for SOC of same frequency, and alphabetically for PT of same frequency.

Reference Listing: 16.2.7.6

Programming Notes:

- Same shell as Table 14.3.1.2. Change first row to be "Subjects with at Least One Anaphylactic Reaction, Hypersensitivity or Infusion-Related Reactions Leading to Discontinuation of IP". Remove references to TEAEs in footnote.
- Update Reference Listing to 16.2.7.6.
- A column for column dosing (column dosing (column dosing (column dosing (column dosing dosi

Final 1.2 | 04-Oct-2023 | Page 82 of 218

[figure not shown]
6.4. Laboratory Data

Table 14.3.4.1
Descriptive Summary of Clinical Chemistry
Safety Population

Parameter: xxxxx (unit)

	Placebo		MEDI7352			Total
Visit/		CCI	CCI	CCI	All MEDI7352	
Statistic	(N=xx)	(N=xx)	(N=xx)	(N=xx)	(N=xx)	(N=xx)
Baseline [1]						
n	XX	XX	XX	XX	XX	XX
Mean (SD)	xx.x (xx.xx)					
Median	XX.X	XX.X	XX.X	XX.X	XX.X	XX.X
Q1, Q3	XX.X, XX.X					
Min, Max	XX, XX					
Low NCS	x (xx.x%)					
Low CS	x(xx.x%)	x (xx.x%)				
Normal	x (xx.x%)					
High NCS	x (xx.x%)					
High CS	x (xx.x%)					
Day 1						
n	XX	XX	XX	XX	XX	XX
Mean (SD)	xx.x(xx.xx)	xx.x(xx.xx)	xx.x(xx.xx)	xx.x (xx.xx)	xx.x(xx.xx)	xx.x (xx.xx)
Median	XX.X	XX.X	XX.X	XX.X	XX.X	XX.X
Q1, Q3	XX.X, XX.X					
Min, Max	XX, XX					
Low NCS	x (xx.x%)					
Low CS	x (xx.x%)					
Normal	x(xx.x%)	x (xx.x%)	x (xx.x%)	x (xx.x%)	x(xx.x%)	x (xx.x%)
High NCS	x (xx.x%)					
High CS	x (xx.x%)					

Final 1 2 | 04-Oct-2023 | Page 83 of 218

Day 1 CFB

n	XX	XX	XX	XX	XX	XX
Mean (SD)	xx.x (xx.xx)	xx.x(xx.xx)	xx.x(xx.xx)	xx.x(xx.xx)	xx.x(xx.xx)	xx.x(xx.xx)
Median	xx.x	XX.X	XX.X	XX.X	XX.X	XX.X
Q1, Q3	XX.X, XX.X	XX.X, XX.X	XX.X, XX.X	XX.X, XX.X	XX.X, XX.X	XX.X, XX.X
Min, Max	XX, XX	XX, XX	XX, XX	XX, XX	XX, XX	XX, XX

CFB = change from baseline; CS = clinically Significant; n = number of subjects by treatment group at each visit for the parameter; N = number of subjects per treatment group; NCS = not clinically significant; SD = standard deviation; Q1 = first quartile; Q3 = third quartile.

Note: Percentages are n/Number of subjects with not missing data by treatment group at each visit*100.

Reference Listing: 16.2.8.1

Programming Notes:

- Present only scheduled visits.
- Sort Parameters in the following Order: Albumin, Alkaline Phosphatase, Alanine Aminotransferase (ALT), Aspartate Aminotransferase (AST), Bicarbonate, Calcium, Chloride, Creatinine, High-Sensitivity C-Reactive Protein (hs-CRP), Estimated Glomerular Filtration Rate (eGFR by Cockcroft-Gault), Serum Glucose, Lactate Dehydrogenase (LDH), Potassium, Sodium, Total Bilirubin, Total Protein, Blood Urea Nitrogen (BUN), Uric Acid.
- A column for column dosing (column dosing (column dosing (column dosing (column dosing dosi

Final 1 2 | 04-Oct-2023 | Page 84 of 218

^[1] Baseline is defined as the last observation recorded prior to the first dose of treatment.

[figure not shown]

Table 14.3.4.2 Shift Table of Clinical Chemistry Results Safety Population

Parameter (Unit)/	_				Baseline	Grade [1]				
Visit			Placebo				MEI	DI7352, CC		
Post-Baseline			(N=xxx)					(N=xxx)		
Grade	Low	Normal	High	Missing	Total	Low	Normal	High	Missing	Total
XXXXXX (Unit)										
Week x										
Low	x (xx.x%)	x (xx.x%)	x(xx.x%)	x(xx.x%)	x(xx.x%)	x(xx.x%)	x(xx.x%)	x(xx.x%)	x(xx.x%)	x (xx.x%)
Normal	x(xx.x%)	x (xx.x%)	x(xx.x%)	x(xx.x%)	x(xx.x%)	x (xx.x%)	x(xx.x%)	x (xx.x%)	x(xx.x%)	x (xx.x%)
High	x(xx.x%)	x(xx.x%)	x(xx.x%)	x(xx.x%)	x(xx.x%)	x (xx.x%)	x (xx.x%)	x(xx.x%)	x(xx.x%)	x (xx.x%)
Missing	x(xx.x%)	x (xx.x%)	x (xx.x%)	x (xx.x%)	x (xx.x%)	x(xx.x%)	x (xx.x%)	x (xx.x%)	x (xx.x%)	x (xx.x%)
Total	x (xx.x%)	x (xx.x%)	x (xx.x%)							
Week x										
Low	x (xx.x%)	x(xx.x%)	x (xx.x%)	x (xx.x%)	x (xx.x%)	x (xx.x%)				
Normal	x (xx.x%)	x(xx.x%)	x (xx.x%)	x (xx.x%)	x(xx.x%)	x (xx.x%)				
High	x (xx.x%)	x (xx.x%)	x(xx.x%)	x(xx.x%)	x (xx.x%)	x(xx.x%)	x (xx.x%)	x (xx.x%)	x (xx.x%)	x (xx.x%)
Missing	x (xx.x%)	x(xx.x%)	x (xx.x%)	x (xx.x%)	x(xx.x%)	x (xx.x%)				
Total	x (xx.x%)	x (xx.x%)	x (xx.x%)	x(xx.x%)	x(xx.x%)	x (xx.x%)	x (xx.x%)	x(xx.x%)	x(xx.x%)	x (xx.x%)

n = number of subjects within each category; N = number of subjects per treatment group.

Percentages are n/Number of subjects by treatment group at each visit for the parameter*100.

Reference Listing 16.2.8.1

Programming Notes:

- Repeat above in new pages for MEDI7352, CC MEDI7352, CC and All MEDI7352.
- Repeat the above for dosing only if Stage 4 is initiated.
- Repeat for every scheduled visit.
- Present parameters in the same order as in Table 14.3.4.1.

Final 1 2 | 04-Oct-2023 | Page 85 of 218

^[1] Baseline is defined as the last observation recorded prior to the first dose of treatment.

[figure not shown]

Table 14.3.4.3 Descriptive Summary of Hematology Safety Population

Programming Notes:

- Same shell as Table 14.3.4.1
- Present only scheduled visits.
- Sort Parameters in the following Order: Absolute basophil count, absolute eosinophil count, absolute lymphocytes count, Absolute Monocyte Count, Absolute Neutrophil Count, Basophils %, Eosinophils %, Hematocrit (HCT), Hemoglobin (HGB), hemoglobin A1C (HgbA1C), Lymphocytes %, mean corpuscular hemoglobin (MHC), Mean Corpuscular Hemoglobin Concentration (MCHC), Mean Corpuscular Volume (MCV), Monocytes %, Neutrophils %, Platelets, Red blood cell count (RBC), Red Cell Distribution Width, white blood cell Count (WBC).
- Update Reference listing to 16.2.8.2.
- A column for column for column dosing (column dosing (column for column for

Table 14.3.4.4 Shift Table of Hematology Results Safety Population

Programming Notes:

- Same shell as Table 14.3.4.2
- Repeat the shell for column dosing if Stage 4 is initiated.
- Repeat for every scheduled visit.
- Present parameters in the same order as in Table 14.3.4.3.
- Update Reference listing to 16.2.8.2

Final 1 2 | 04-Oct-2023 | Page 86 of 218

[figure not shown]

Table 14.3.4.5 Descriptive Summary of Coagulation Safety Population

Programming Notes:

- Same shell as Table 14.3.4.1
- Present only scheduled visits.
- Sort Parameters in the following Order: Activated Partial Thromboplastin Clotting Time (APTT), Fibrinogen, International normalized ratio (INR), Prothrombin Time (PT).
- Update Reference listing to 16.2.8.3.
- A column for column for column dosing (column for column for col

Table 14.3.4.6 Shift Table of Coagulation Results Safety Population

Programming Notes:

- Same shell as Table 14.3.4.2
- Repeat for column dosing if Stage 4 is initiated.
- Repeat for every scheduled visit.
- Present parameters in the same order as in Table 14.3.4.5.
- Update Reference listing to 16.2.8.3.

Final 1 2 | 04-Oct-2023 | Page 87 of 218

[figure not shown]

[figure not shown]

Table 14.3.4.7 Descriptive Summary of Urinalysis Safety Population

Parameter: xxxxx (unit)

	Placebo		MEDI7352			Total
Visit/		CCI	CCI	CCI	All MEDI7352	
Statistic	(N=xx)	(N=xx)	(N=xx)	(N=xx)	(N=xx)	(N=xx)
Baseline [1]						
n	XX	XX	XX	XX	XX	XX
Mean (SD)	xx.x(xx.xx)	xx.x(xx.xx)	xx.x(xx.xx)	xx.x(xx.xx)	xx.x(xx.xx)	xx.x (xx.xx)
Median	xx.x	XX.X	XX.X	XX.X	XX.X	XX.X
Q1, Q3	xx.x, xx.x	XX.X, XX.X	XX.X, XX.X	XX.X, XX.X	XX.X, XX.X	XX.X, XX.X
Min, Max	XX, XX	XX, XX	XX, XX	XX, XX	xx, xx	xx, xx
Low NCS	x(xx.x%)	x(xx.x%)	x(xx.x%)	x(xx.x%)	x(xx.x%)	x(xx.x%)
Low CS	x (xx.x%)	x(xx.x%)	x(xx.x%)	x(xx.x%)	x(xx.x%)	x(xx.x%)
Normal	x (xx.x%)	x(xx.x%)	x(xx.x%)	x(xx.x%)	x(xx.x%)	x(xx.x%)
High NCS	x (xx.x%)	x(xx.x%)	x (xx.x%)	x (xx.x%)	x(xx.x%)	x (xx.x%)
High CS	x (xx.x%)	x (xx.x%)	x (xx.x%)	x (xx.x%)	x (xx.x%)	x (xx.x%)
Day 1						
n	XX	XX	XX	XX	XX	XX
Mean (SD)	xx.x(xx.xx)	xx.x(xx.xx)	xx.x(xx.xx)	xx.x(xx.xx)	xx.x(xx.xx)	xx.x (xx.xx)
Median	XX.X	XX.X	XX.X	XX.X	XX.X	XX.X
Q1, Q3	xx.x, xx.x	XX.X, XX.X	XX.X, XX.X	XX.X, XX.X	XX.X, XX.X	XX.X, XX.X
Min, Max	XX, XX	XX, XX	XX, XX	XX, XX	xx, xx	xx, xx
Low NCS	x (xx.x%)	x(xx.x%)	x(xx.x%)	x(xx.x%)	x(xx.x%)	x(xx.x%)
Low CS	x (xx.x%)	x (xx.x%)	x (xx.x%)	x(xx.x%)	x(xx.x%)	x (xx.x%)
Normal	x (xx.x%)	x(xx.x%)	x(xx.x%)	x(xx.x%)	x(xx.x%)	x(xx.x%)
High NCS	x (xx.x%)	x(xx.x%)	x(xx.x%)	x(xx.x%)	x(xx.x%)	x (xx.x%)
High CS	x (xx.x%)	x (xx.x%)	x (xx.x%)	x (xx.x%)	x (xx.x%)	x (xx.x%)
Day 1 CFB						
n	XX	XX	XX	XX	XX	XX
Mean (SD)	xx.x (xx.xx)	xx.x(xx.xx)	xx.x(xx.xx)	xx.x(xx.xx)	xx.x(xx.xx)	xx.x (xx.xx)
Median	xx.x	XX.X	XX.X	XX.X	XX.X	XX.X
Q1, Q3	XX.X, XX.X	XX.X, XX.X	XX.X, XX.X	XX.X, XX.X	XX.X, XX.X	XX.X, XX.X
Min, Max	xx, xx	xx, xx	XX, XX	xx, xx	xx, xx	xx, xx

Final 1 2 | 04-Oct-2023 | Page 88 of 218

..

Repeat for all visits for Parameters: Specific Gravity and pH

Baseline [1]						
n	XX	XX	XX	XX	XX	XX
Negative	x(xx.x%)	x(xx.x%)	x(xx.x%)	x(xx.x%)	x(xx.x%)	x(xx.x%)
Positive	x(xx.x%)	x(xx.x%)	x (xx.x%)	x(xx.x%)	x(xx.x%)	x(xx.x%)
Normal	x(xx.x%)	x(xx.x%)	x(xx.x%)	x(xx.x%)	x(xx.x%)	x(xx.x%)
High NCS	x(xx.x%)	x(xx.x%)	x (xx.x%)	x (xx.x%)	x (xx.x%)	x (xx.x%)
High CS	x (xx.x%)					
If Positive, Specify [2]						
100 mg/dL	x(xx.x%)	x(xx.x%)	x(xx.x%)	x(xx.x%)	x(xx.x%)	x(xx.x%)
250 mg/dL	x(xx.x%)	x(xx.x%)	x (xx.x%)	x(xx.x%)	x(xx.x%)	x (xx.x%)
500 mg/dL	x(xx.x%)	x(xx.x%)	x(xx.x%)	x(xx.x%)	x (xx.x%)	x (xx.x%)
>= 1000 mg/dL	x (xx.x%)	x (xx.x%)	x (xx.x%)	x(xx.x%)	x (xx.x%)	x (xx.x%)
Day 1						
n	XX	XX	XX	XX	XX	XX
Negative	x(xx.x%)	x(xx.x%)	x(xx.x%)	x(xx.x%)	x(xx.x%)	x(xx.x%)
Positive	x(xx.x%)	x(xx.x%)	x(xx.x%)	x(xx.x%)	x(xx.x%)	x(xx.x%)
Normal	x(xx.x%)	x(xx.x%)	x(xx.x%)	x(xx.x%)	x(xx.x%)	x (xx.x%)
High NCS	x(xx.x%)	x (xx.x%)	x (xx.x%)	x(xx.x%)	x(xx.x%)	x (xx.x%)
High CS	x (xx.x%)	x (xx.x%)	x (xx.x%)	x(xx.x%)	x (xx.x%)	x (xx.x%)

•••

Repeat for all visits for Parameters: Blood, Glucose, Ketones and Protein

CFB = change from baseline; CS = clinically significant; n = number of subjects by treatment group at each visit for the parameter; N = number of subjects per treatment group; NCS = not clinically significant; SD = standard deviation; Q1 = first quartile; Q3 = third quartile.

[figure not shown]
Note: Percentages are n/Number of subjects with not missing data by treatment group at each visit*100.

Reference Listing: 16.2.8.4

Final 1 2 | 04-Oct-2023 | Page 89 of 218

^[1] Baseline is defined as the last observation recorded prior to the first dose of treatment.

^[2] Percentages are n/Number of Subjects with a Positive Result*100.

Programming Notes:

- Present only scheduled visits.
- Sort Parameters in the following Order: Blood Urine, Glucose, Ketones, pH, Protein, Specific Gravity.
- Categories for If Positive, Specify:
 - o Blood, Urine: Trace, Small, Moderate.
 - $\odot \quad Glucose: 100 \ mg/dL, 250 \ mg/dL, 500 \ mg/dL, >= 1000 \ mg/dL.$
 - o Ketones: Trace, 15 mg/dL, 40 mg/dL.
 - o Protein: Trace, 30 mg/dL, 100 mg/dL, 300 mg/dL.
- A column for column dosing (column dosing will only be added if Stage 4 is initiated.

Final 1 2 | 04-Oct-2023 | Page 90 of 218

[figure not shown]

Table 14.3.4.8 Shift Table of Urinalysis Results Safety Population

Programming Notes:

- Same shell as Table 14.3.4.2
- Repeat for dosing if Stage 4 is initiated.
- Repeat for every scheduled visit.
- Present parameters in the same order as in Table 14.3.4.7.
- Update Reference listing to 16.2.8.4

Final 1 2 | 04-Oct-2023 | Page 91 of 218

[figure not shown]

Table 14.3.4.9

Maximum On-Treatment ALT and AST versus Maximum On-Treatment Total Bilirubin Safety Population

			Total F	Bilirubin
			<2 x ULN	>=2 x ULN
Group	Nobs		n (%)	n (%)
Placebo				
N=xxx	XXX	ALT		
		<3 x ULN	x (xx.x%)	x (xx.x%)
		>=3 - <5 x ULN	x (xx.x%)	x (xx.x%)
		>=5 -<10 x ULN	0	0
		>=10 x ULN	0	0
	xxx	AST		
		<3 x ULN	x (xx.x%)	x (xx.x%)
		>=3 - <5 x ULN	x (xx.x%)	x (xx.x%)
		>=5 -<10 x ULN	0	0
		>=10 x ULN	0	0

Repeat for: CC

[figure not shown]
All MEDI7352

ALT = a lanine aminotransferase; AST = a spartate a minotransferase; IP = investigational product; n = number of subjects per category; N = number of subjects per treatment group; Nobs = number of subjects per treatment group with at least one post-baseline assessment on treatment; ULN = upper limit of normal.

Note: On-treatment assessments include assessments on or after the date of first dose of IP. Baseline is defined as the last observation recorded prior to the first dose of treatment.

Percentages are based on Nobs.

Reference Listing: 16.2.8.1

[figure not shown]

Programming Notes:

• Per Protocol, the elevations of ALT or AST and Total Bilirubin do not have to occur at the same time or within a specified time frame. That is the reason why the table is presented by Subject instead of by visit. So, if for example, one subject has ALT >= 3 - <5 x ULN at Day 1, and TBL >= 2 x ULN at Week 18, n in that cell will increase by one.

• A column for dosing (CC) will only be added if Stage 4 is initiated.

Final 1 2 | 04-Oct-2023 | Page 93 of 218

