- Update footnote: Anaphylactic reactions, hypersensitivity or infusion-related reactions not leading to discontinuation of IP were included in listing as they were categorized as AE of special interest under Protocol Amendment 4 (V5.0). Definition for AE of special interest changed from Amendment 6 (V6.0) onwards, including an applylactic reactions, hypersensitivity or infusion-related reactions leading to permanent discontinuation of IP.

Final 1 2 | 04-Oct-2023 | Page 164 of 218

Listing 16.2.8.1 Clinical Chemistry Laboratory Evaluations Safety Population

Subject ID/ Treatment Arm	Parameter	Study Visit	Date/Time of Collection (Study Day)	Original Result (Unit)	Standard Results (unit)	Reference Range [1]	Baseline Flag	CFB	Results Assessment / Reason CS	Lab ID Number	Fasting Status	Comments
XXXXX/ XXXX	Chemistry panel	XXXXXX							ND: xxx			
XXXXX/ XXXX	Albumin	XXXXXX XXXXXX XXXXXX XXXXXX	DDMMMYYYY/ HH:MM (X) DDMMMYYYY/ HH:MM (X) DDMMMYYYY/ HH:MM (X) DDMMMYYYY/ HH:MM (X)	XX (XX) XX (XX) XX (XX) XX (XX)	XX (XX) XX (XX) XX (XX) XX (XX)	XX - YY XX - YY XX - YY XX - YY	Y	XX.X XX.X XX.X	H-CS / XXX H-NCS	XXXXXXX XXXXXXX XXXXXXX XXXXXXX	Y Y Y N	XXXX

CFB = change from baseline; CS = clinically significant; H = High; L = Low; NCS = not clinically significant; ND = not done.

Note: Study Day is calculated relative to the date of first dose.

[figure not shown]
Baseline is defined as the last observation recorded prior to the first dose of treatment.

[1] Reference range is used to identify potentially clinically significant laboratory values.

Programming Notes:

- Keep parameter sorting from the last bullet point below.
- For results assessment, do not populate column if result is normal.
- Sort by Treatment Arm/ Subject ID / Parameter / Date time of collection.
- If the whole panel is not done at a visit, present the information on first row of the subject under 'Chemistry panel' parameter and don't present the 'not done' information for each parameter. Display "ND: reason why" in the result assessment column.
- Sort Parameters in the following Order: Albumin, Alkaline Phosphatase, Alanine Aminotransferase (ALT), Aspartate Aminotransferase (AST), Bicarbonate, Calcium, Chloride, Creatinine, High-Sensitivity C-Reactive Protein (hs-CRP), Estimated Glomerular Filtration Rate (eGFR by Cockcroft-Gault), Serum Glucose, Lactate Dehydrogenase (LDH), Potassium, Sodium, Total Bilirubin, Total Protein, Blood Urea Nitrogen (BUN), Uric Acid.

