- Concatenate all Symptoms by "/"
- Sort by Treatment Arm/ Subject ID / Date of assessment

Final 1 2 | 04-Oct-2023 | Page 172 of 218

Listing 16.2.9.1 Vital Signs Measurements Safety Population

Subject ID	Treatment Arm	Parameter	Study Visit	Position [1] / T° Method	Date/Time of Collection (Study Day)	Original Result (Unit)	Baseline Flag	CFB
XXXXX	XXXX	Body Temperature	XXXXXX	XXXX	DDMMMYYYY/ HH:MM (X)	XX (XX)	Y	
		I	XXXXXX	XXXX	DDMMMYYYY/ HH:MM (X)	XX (XX)		XX
						•••		
		Resting Heat Rate	Screening	Supine	DDMMMYYYY/ HH:MM (X)	XX		
		1100011000	Day 1: Pre-Dose	Supine	DDMMMYYYY/ HH:MM (X)	XX	Y	XX
			XXXXXX	Supine	DDMMMYYYY/ HH:MM (X)	XX		XX
			XXXXXX XXXXXX	Sitting Sitting	DDMMMYYYY/ HH:MM (X)	ND XX		XX

CFB = change from baseline; eCRF = Electronic Case Report Form; ND = not done.

[figure not shown]
Note: Study Day is calculated relative to the date of first dose.

Baseline is defined as the last observation recorded prior to the first dose of treatment.

'Day 1:5 minutes after Infusion Completion' time point was only applied to subjects enrolled in Stage 1, with data collected under eCRF versions 4.0 (11DEC2018) or older.

[1] Resting position measurements encompass Sitting and Supine position measurements.

Final 1 2 | 04-Oct-2023 | Page 173 of 218

[figure not shown]

Programming Notes:

- Sort by Treatment Arm/ Subject ID / Parameter (Order in the second bullet point)/ Date time of collection.
- Repeat for Resting Heart Rate, Resting Systolic Blood Pressure, Resting Dia stolic Blood Pressure, Respiratory Rate, Body Temperature, Standing Heart Rate, Standing Systolic Blood Pressure, Standing Dia stolic Blood Pressure.
- After Week 2 (inclusive), Supine measure are taken in sitting position. We will consider them as supine (in resting position) for calculating Change from Baseline (always at supine position).
- Include the following timepoints: Screening, Baseline (Day 1: Pre-Dose), Day 1: 15 Minutes Post-Dose, Day 1: 30 Minutes Post-Dose, Day 1: 45 Minutes Post-Dose, Day 1: 1 hour Post-Dose, Day 1: 2 hours Post-Dose, Day 1: 4 hours Post-Dose, Week 2: Pre-Dose, Week 2: 5 minutes a fter Infusion Completion, Week 4: Pre-Dose, Week 4: 5 minutes a fter Infusion Completion, Week 6: Pre-Dose, Week 6: 5 minutes after Infusion Completion, Week 8: Pre-Dose, Week 8: 5 minutes after Infusion Completion, Week 10: Pre-Dose, Week 10: 5 minutes after Infusion Completion, Week 11, Week 12, Week 18.

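### Table 14.3.4.9 defines on-treatment by calendar date, so a chemistry sample taken before the infusion on the dosing day would be both baseline and on-treatment

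*SAP*

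**What the plan says.** SAP section 6.4 contains Table 14.3.4.9, titled "Maximum On-Treatment ALT and AST versus Maximum On-Treatment Total Bilirubin Safety Population". It places each subject once for ALT and once for AST, by the highest transaminase category (below 3, 3 to below 5, 5 to below 10, and 10 or more times ULN) against the highest bilirubin category (below 2, and 2 or more times ULN).

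Four statements under the table bear on which samples count:

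- The selection rule: "On-treatment assessments include assessments on or after the date of first dose of IP".
- The baseline rule, in the next sentence: "Baseline is defined as the last observation recorded prior to the first dose of treatment".
- The denominator: "Nobs = number of subjects per treatment group with at least one post-baseline assessment on treatment".
- The programming note's example of a subject who is counted: "one subject has ALT >= 3 - <5 x ULN at Day 1, and TBL >= 2 x ULN at Week 18". It does not say whether the Day 1 sample precedes or follows the infusion.

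The wording is the same in the Draft 1.1 shells of 31 August 2023 and the Final 1.2 shells of 4 October 2023.

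**The concern.** The two rules use different clocks. The on-treatment rule looks only at the date and includes the dosing date itself. The baseline rule looks at whether the sample came before or after the dose. On the dosing day they can give the same sample both labels, and the table has no rule to separate them.

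This matters more for a maximum than for a by-visit summary. One value carried into the maximum fixes the subject's row or column for the whole study. The programming note also makes clear that the transaminase and bilirubin elevations need not coincide, so a transaminase value present before any exposure could be paired with a bilirubin value many weeks later. The subject would then appear in a combined-elevation cell headed as on-treatment, although the transaminase elevation predated the drug.

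**Working it through.** No sample size, power or error rate is involved and the plan gives no figure to reproduce. The check applies the two definitions to one sample and then works out when the table changes.

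**Step 1. Do the definitions overlap?** Take a chemistry sample drawn on the date of first dose but before the infusion, with no later pre-dose sample.

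| Rule in the footnote | What it tests | Result |
|---|---|---|
| On-treatment | Sample date on or after the dosing date | Met, because the dates are equal |
| Baseline | Last sample before the dose | Met |

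The sample is in both sets.

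**Step 2. Does the denominator rule resolve it?** No. Nobs requires a subject to have a post-baseline sample. That decides who is in the denominator, not which of the subject's values enter the maximum. It suggests baseline values were meant to stay out, but the numerator rule does not say so.

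**Step 3. When does a cell change?** Let x0 be the pre-dose value on the dosing day and M the highest value after the first infusion has started.

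- Date rule: maximum = max(x0, M).
- Time rule: maximum = M.

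Since max(x0, M) is never below M, the date rule can only move a subject to a higher category or leave the subject in place. The category differs only when x0 lies in a higher category than M. Three cases for ALT, with assumed values:

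| Pre-dose ALT on Day 1 | Later ALT | Bilirubin | Cell under date rule | Cell under time rule |
|---|---|---|---|---|
| 3.5 x ULN | all below 3 x ULN | 2.1 x ULN at Week 18 | ALT 3 to <5, bilirubin 2 or more | ALT <3, bilirubin 2 or more |
| 3.5 x ULN | highest also between 3 and 5 x ULN | 2.1 x ULN at Week 18 | ALT 3 to <5, bilirubin 2 or more | same |
| below 3 x ULN | any | 2.1 x ULN at Week 18 | set by later ALT | same |

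Only the first case is misclassified. The same logic holds for AST and for bilirubin.

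**Step 4. Can a pre-dose Day 1 chemistry sample exist?** The document does not settle this.

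- In favour: pre-dose assessment on Day 1 is routine elsewhere in the trial. The vital signs listing (16.2.9.1) has "Baseline (Day 1: Pre-Dose), Day 1: 15 Minutes Post-Dose", the ECG listings have a pre-dose Day 1 point, and the serum concentration tables label Day 1 as baseline.
- Against: Table 14.3.4.1 shows Day 1 chemistry as a block separate from baseline, with its own change from baseline. If Day 1 were the baseline draw, that change would be zero for every subject.

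**Step 5. Is a better rule feasible?** Yes. Listing 16.2.8.1 has a column headed "Date/Time of Collection (Study Day" and a baseline flag. The plan's definition of a treatment-emergent adverse event, in the notes to Table 14.3.1.1, already turns on the start of treatment and not on its calendar date.

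**The case against.** The strongest reply is that the overlap may be empty. The separate Day 1 block in Table 14.3.4.1 leans towards Day 1 chemistry not being the baseline draw, and the visit schedule that would settle it is not shown. That stands, and it is why the point is conditional. The example with "one subject has ALT >= 3 - <5 x ULN at Day 1" illustrates that elevations need not be simultaneous. It does not show that a baseline value is intended to count, only that nothing in it rules one out.

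A second reply is that only part 2 of the SAP is at hand and the body may define on-treatment properly. That is possible. Even so, this footnote states its own rule without deferring to another section, and a programmer would follow it.

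A third reply is that the table is descriptive. Potential Hy's Law cases are tracked by case number in Listings 16.2.9.10 to 16.2.9.12, the chemistry listing flags the baseline record, the shift table crosses baseline with later grade, and the same rule applies to placebo. This also stands and limits the severity, although the shift table grades only low, normal and high and so does not show the multiples of ULN used here.

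Two stronger readings are tempting and not supported. A reader might infer that a subject whose only sample is pre-dose would enter the denominator. The Nobs definition excludes that subject, because the sample is the baseline and there is no post-baseline sample. A reader might also want to state the effect as percentage points per affected subject in an arm. The shells give no arm sizes, and not every subject with a pre-dose elevation changes cell.

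**Conclusion.** The footnote contradicts itself for samples taken on the dosing day before the infusion: they would be both baseline and on-treatment, and nothing in the shown text keeps them out of the maxima.

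The size depends on a fact the document does not give. If all Day 1 chemistry is post-dose, the effect is nil. If some or all is pre-dose, the subjects affected are those whose pre-dose ALT, AST or bilirubin falls in a higher category than every later value. The direction is over-counting only.

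It would go too far to say that the plan does report pre-existing elevations as on-treatment; it would do so only if pre-dose samples exist on the dosing day. The point is minor: a clarification to a descriptive safety table, worth making because the stated rule could mislabel a subject in the combined-elevation cells.

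**What to change.** Make three edits to Table 14.3.4.9:

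1. Define on-treatment as a collection date and time after the start of the first infusion. For Day 1 samples with a missing time, state that the visit schedule decides whether they are pre-dose or post-dose.
2. State that the record flagged as baseline does not enter the maxima. This brings the numerator into line with the denominator definition.
3. In the programming note, mark the Day 1 ALT in the example as post-dose.

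The cost is a line in the derivation and two wording changes. No new data are needed, since collection time and the baseline flag are already planned in Listing 16.2.8.1. If the visit schedule shows that every Day 1 chemistry sample is post-dose, the results will not change.
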